5 ANALYSIS POPULATIONS

5.1 Randomized Population

All subjects randomized will be used for summaries of subject disposition.

5.2 Safety Population

The safety population includes all randomized subjects who received at least 1 dose of study medication. This population is defined for safety analysis. Subjects will be analyzed based on the actual treatment received. The safety population will be used for all analyses of safety endpoints.

5.3 Modified Intent To Treat Population

The modified intent to treat (MITT) population (full analysis population in protocol) includes all randomized subjects who received at least 1 dose of study medication and provided any post baseline seizure outcome data. The MITT population is the primary population for efficacy analysis. Subjects will be analyzed based on their randomized treatment assignment.

5.4 Per Protocol Population

The per protocol (PP) population includes all MITT subjects who received at least 1 dose of treatment without major protocol violations that would potentially impact efficacy. The PP population is used for supportive efficacy analyses. PP population will be finalized by the study team prior to database lock. Per protocol analysis will be conducted on the primary and key-secondary end-points only.

5.5 Protocol Deviations

Major protocol violations leading to exclusion from the per protocol population will be determined prior to unblinding.

6 GENERAL ASPECTS FOR STATISTICAL ANALYSIS

6.1 General Methods

- All analyses and summaries will be produced using SAS version 9.2 or above.
- Unless otherwise specified, summaries will be presented by cohort, treatment and overall.
- Continuous variables will be summarized by number of subjects, mean, standard deviation, median, minimum, and maximum.
- Categorical variables will be summarized by counts and percentages.

6.2 Key Definitions

Calculation of Baseline:

For the primary efficacy endpoint(s):

For subjects enrolled under and prior to Amendment 2, baseline will be calculated based upon a combination of 4 weeks of prospective recording in a daily seizure calendar contiguous with 4 weeks of retrospective seizure history (seizure diary) which will be collected after obtaining informed consent. Acceptable retrospective daily seizure data include a diary record of the frequency and type of seizures by day, subjects without acceptable retrospective daily seizure data will not be randomized. After completing the 4-week prospective baseline period, eligible subjects are to be randomized to receive either ganaxolone or placebo.

For subjects enrolled under Amendment 3, baseline will be calculated based upon the 8 weeks prospective recording in a daily seizure calendar, which will be collected after obtaining informed consent.

For subjects still in the study at time of the primary analysis, last dose date will be considered the date of the most recent DB study visit in the database for that subject.

For safety endpoints, non-missing value of last assessment before first dose will be set as baseline value for both Cohort 1 and Cohort 2.

See Tables 1 and 2 in the protocol for details of the dosing regimen for each cohort/phase.

6.3 Missing Data

If a subject has missing seizure count information during the baseline or treatment periods, these days will be not be imputed or considered in the calculation of the seizure frequency (i.e., the seizure frequency will be computed only over the non-missing days of the period).

If a subject withdraws from the study before the end of the treatment period, the seizure information collected up until the time of withdrawal will be used to calculate the seizure frequency over the treatment period.

However, a set of sensitivity analyses will be conducted as outlined below to understand the impact of missing data due to subject withdrawal from the study.

Imputation of Missing Diary Seizure Frequency Data

The imputation process consists of a sequence of multiple imputation (MI) steps, with each step imputing missing values at one time-point only. The approach differentiates those who withdrew for treatment-related reasons (lack of efficacy or adverse events) and those who withdrew for other reasons (e.g. withdrawal of consent due to a move).

A. Dropout Reason-based Multiple Imputation (DRMI)

The not missing at random (NMAR) model assumes that observed data obtained from the pre-specified subset of withdrawn GNX subjects who dropped out for treatment-related reasons are correlated with unobserved future visits similar to subjects in the placebo arm. This is equivalent to assuming that the unobserved trajectory of patients in the GNX arm is similar to that of the placebo subjects. Treatment related reasons include AEs, death and insufficient clinical response.

B. Dropout Missing at Random Imputation (MAR)

The missing data of the remaining GNX patients who have dropped out (due to non-treatment-related reasons) are imputed assuming MAR. Missing data for placebo patients who withdrew for any reason will always be imputed based on placebo diary seizure frequency data.

A summary of reasons for patients withdrawing from the GNX treatment arm and the corresponding treatment arm used to calculate the imputation of diary seizure frequency data under DRMI will be populated after the blind is broken as shown in the Table below.

The MNAR imputation is achieved by using prior data and previously imputed values at each stage of the imputation. Imputation will be carried out in two steps; first, the non-monotone (intermediate—having a previous and subsequent observation) missing seizure frequencies will be imputed based on a Markov chain Monte Carlo (MCMC) method using SAS PROC MI. Next, missing values in each period will be imputed using a sequential regression method using MONOTONE REG option of SAS PROC MI. The lengths of the period will be two weeks.

For example, to impute missing values in a two week period ending at time t for subjects in the GNX arms who dropped out due to one of treatment related reasons, placebo observations up to and including time t and observations from subjects in the GNX arms who dropped out due to one of the treatment related reasons, up to and including time $t-1$ will be used to develop the model. This is repeated sequentially for each bi-weekly time period using observed data and previously imputed values in the new model.

Ten replicate study imputations will be carried out using a seed of 123456. The analysis of each of the imputed dataset will be based on rank ANCOVA, the analytical method described in the [Section 8.1](#) of the primary analysis; these imputations will be combined using Rubin's formula implemented in the SAS procedure PROC MIANALYZE.

Reason for withdrawal	DRMI
Adverse Event	Placebo
Insuff. clinical response	Placebo
Death	Placebo
Non-compliance or Protocol Violation	GNX
Ineligible Per Inclusion/Exclusion Criteria	GNX
Lost to follow up	GNX
Withdrawal of Consent By Subject	GNX
Other	GNX

6.4 Visit Windows

Subjects must have a minimum of 28 days of prospective baseline seizure charting. Visit windows are time intervals between the mid-points of 2 consecutive scheduled visits for Phase 1 DB and Phase 2 OL (Visits 2- Post taper Safety Follow up) .

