9.4.5 Study Dosing and Dosage Adjustments

Double-blind Phase:

Cohort 1: The study drug dose will be titrated from 400 mg/day to 1200 mg/day in divided doses BID by the end of Week 1 and maintained to Week 5. Dosage will be increased to 1800 mg/day Week 6 and maintained through Week 9 (Table 1).

Cohort 2: The study drug dose will be titrated from 450 mg/day to 1800 mg/day in divided doses BID by the end of Week 2 and maintained through Week 14 (Table 2).

Both titration schedules are consistent with acceptable starting doses and MTDs from previous ganaxolone studies.

Open-Label Phase: Following the completion of the double-blind (DB) phase in either cohort, subjects randomized to placebo will transition to ganaxolone while subjects randomized to ganaxolone will stay on 1800 mg/d. Cohort 1 placebo subjects will begin the 1-week dose titration to 1800 mg/d after completing their Visit 5. Subjects will receive ganaxolone 900 mg/d in divided doses BID for 2 days and step up to 1350 mg for 3 days and then increase to 1800 mg in divided doses BID for 2 days until their Visit 6 (Table 1). Titration for Cohort 2 placebo subjects will mirror the DB phase. Subjects will begin the 2-week dose titration to 1800 mg/d after completing their Visit 5. Subjects will start with 450 mg/d in divided doses BID for 3 days, 900 mg/d in divided doses BID for 3 days, 1350 mg/d in divided doses BID for 4 days, and 1800 mg/d in divided doses BID for 4 days until their Visit 6 (Table 2). At Visit 6, all subjects in both cohorts will be evaluated for tolerability and the investigator will make the determination to maintain the subject on 1800 mg/d or adjust their dose. If the patient experiences any tolerability issues during the transition to OL, such as sedation or dizziness, changes to the titration schedule (e.g., conducting the titration over 3 weeks vs. 2 weeks) may be approved after discussion with the medical monitor. Subjects may be maintained on the MTD of ganaxolone that provides adequate seizure control that is not less than 900 mg/d and not more than 1800 mg/d. Doses may be adjusted upward or downward in 225 mg/d increments every 3 days to reach an optimal dose level over the duration of the 52-week OL phase. Dose adjustments should be made with the investigator's agreement. Frequency of dosing changes may not be less than 3 days unless required for safety.

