9.5.3 Safety Assessments

Planned safety assessments include:

Neurological and physical examinations

Clinical laboratory tests

12-lead ECG

Vital signs including temperature, blood pressure, pulse rate, respiration rate, height, weight and BMI

Columbia Suicide Severity Rating Scale (C-SSRS)

AE monitoring: frequency, severity, duration, causality, outcome

Clinical labs, vitals and ECG measurements may be repeated if needed to corroborate or refute abnormal findings. Both the original and replicate assessments should be recorded in the eCRF.

See [Appendix 1](#) Schedule of Events for timing of Safety Assessments.

Adverse events will be presented for these time periods for Cohorts 1 & 2: ganaxolone vs placebo Titration + Maintenance (Cohort 1: Weeks 1-9, Cohort 2: Weeks 1-14), 1200

mg/d vs placebo (Cohort 1: Weeks 2-5), and 1800 mg/d vs placebo (Cohort 2: Weeks 6-9) for the safety population; open-label (Cohort 1: Weeks 10-61, Cohort 2: 15-66). In addition, tolerability of ganaxolone during the up-titration phases of the study will be compared between the two cohorts. AEs with onset during the titration phase in Cohort 2 will be compared to AEs with onset during the weeks 1-5 in Cohort 1 (1 week titration + 4 week treatment with 1200 mg/day). In addition, in Cohort 2, AEs with onset during the titration phase will be compared to AEs with onset during the maintenance phase. AEs that emerge during the de-escalation period will be tabulated to investigate whether discontinuation of ganaxolone is associated with withdrawal symptoms. Secondary safety outcome measures include those listed below.

Secondary Safety Parameters for Cohorts 1 & 2	Cohort 1		Cohort 2		Combine Cohorts 1 & 2	
	DB Phase	OL Phase	DB Phase	OL Phase	DB Phase	OL Phase
Number of subjects at each dose	X	X	X	X		X
The frequency and proportion of subjects with AEs	X	X	X	X		X
Severity of AEs	X	X	X	X		X
AEs leading to DC	X	X	X	X		X
Incidence of subjects with early DC	X	X	X	X		X
Change from baseline in vital signs (blood pressure, respiration rate and heart rate), body weight and ECG	X	X	X	X		X
Change in clinical hematology and chemistry parameters	X	X	X	X		X
Assessment of suicidality via the Columbia Suicide Severity Rating Scale (C-SSRS)	X	X	X	X		X

Additional assessments may be conducted as considered appropriate.

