9.5.5.3 Visit 3 (Up-Titration; Cohort 1: Week 1; Cohort 2: Week 2)

Concomitant AEDs reviewed; physical and neurological examinations performed; vital signs taken; ECG performed 2-3 hours after dosing; blood samples drawn for hematology, chemistry, and concomitant AED levels; urine sample obtained for urinalysis and pregnancy test for WCBP; Columbia Suicide Scale assessed; AEs assessed; subject calendar reviewed; study medication compliance assessed; study medication dispensed.

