Between DB (Phase 1) and OL (Phase 2) study phases, Cohort 1 has a 1-week, double-blinded, step transition for placebo subjects to 900 mg/d followed by 1800 mg/d while ganaxolone subjects are maintained on their current dose. For the purpose of entering dosing information on the eCRFs, the sites are instructed to assume that all patients transitioning to the OL phase are on placebo and will enter dose-escalation information accordingly. After unblinding K&L will correct the actual dosing, and the patients who were on ganaxolone during the DB phase will be changed to have received 1800 mg/day during the transition period.

Cohort 1, Phase 2 is the OL phase, consisting of 2 treatment phases: Flexible Dosing (51-week flexible dosing during which time the dose may be adjusted based on efficacy and tolerability guidelines), and De-escalation (2 weeks, at study termination). Subjects discontinued during the study will be de-escalated over 2 weeks based on dose, duration, and tolerability in the opinion of the investigator.

Cohort 2, Phase 1 of treatment includes a 14-week DB phase placebo-controlled treatment period to evaluate oral study medication as add-on therapy in adults with epilepsy consisting of POS, with or without secondary generalization. Study subjects will be randomized to one of the 2 study treatment arms: ganaxolone at 1800 mg/d or placebo. Phase 1 (DB phase) is comprised of a Baseline period (8 weeks), followed by 2 treatment periods: Titration (2 weeks up to 1800 mg/d) and Maintenance (12 weeks on 1800 mg/d). Subjects entered into Cohort 2, under

Protocol Amendment 2, will have a baseline assessment based on 4 weeks retrospective and 4 weeks prospective seizure data.

Between the study phases, Cohort 2 has a 2-week, blinded, step transition for placebo subjects to ganaxolone, starting at 900 mg/d to 1800 mg/d, while ganaxolone subjects are maintained on their current dose. For the purpose of entering dosing information on the eCRFs, the sites are instructed to assume that all patients transitioning to the OL phase are on placebo and will enter dose-escalation information accordingly. After unblinding K&L will correct the actual dosing, and the patients who were on ganaxolone during the DB phase will be changed to have received 1800 mg/day during the transition period.

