9.4 Laboratory Evaluations

Laboratory data (including change from baseline) will be summarized using descriptive statistics by treatment and overall for each cohort and phase separately for subjects in the Safety Population. Laboratory data of subjects pooled in Cohort 1 and Cohort 2 for each treatment phase will be summarized. SI units will be used for both summarization and data listings.

Separate summary tables and listings will be produced for each laboratory test group (Hematology, Serum Chemistry, Urinalysis, and other tests: See Protocol Appendix 2: Clinical Laboratory Tests).

Hematology, Serum Chemistry, Urinalysis, and other tests will be summarized for baseline, each visit assessed, and for change from baseline by treatment group using descriptive statistics.

Low, normal, and high classifications will be applied according to the central lab's definitions to determine whether the worst laboratory test value within the visit window was below (low), within (normal), or above (high) its reference range. Shifts from baseline in low/normal/high classification for each parameter will be summarized by treatment group.

If there are multiple records within a visit window the last record will be used for summary tables, all results will be used for tables that assess maximum grade or toxicity, and included in data listings.

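### SAP mid-point visit windows run across treatment changes at Visit 5 (both cohorts) and at Cohort 1 Visit 4, so an unscheduled laboratory record taken after the change can be reported as that visit's value

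*SAP*

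**What the plan says.** - **Window rule.** SAP 6.4 defines windows as follows: "Visit windows are time intervals between the mid-points of 2 consecutive scheduled visits for Phase 1 DB and Phase 2 OL". It has no exception at the end of the double-blind phase or at the Cohort 1 dose step.
- **Record selection.** SAP 9.4 states for laboratory data: "If there are multiple records within a visit window the last record will be used for summary tables". The shift tables instead classify the "worst laboratory test value within the visit window". Neither rule appears in the sections on vital signs or ECG.
- **Treatment changes.** For Cohort 2 placebo subjects, Protocol 9.4.5 states: "Subjects will begin the 2-week dose titration to 1800 mg/d after completing their Visit 5". Cohort 1 placebo subjects likewise switch after Visit 5, and Cohort 1 ganaxolone subjects step from 1200 to 1800 mg/d at Visit 4 (Table 1).
- **Unscheduled samples.** Protocol 9.5.3 states: "Clinical labs, vitals and ECG measurements may be repeated if needed to corroborate or refute abnormal findings". It asks for both original and repeat to be recorded. Protocol 9.3.4.1 item 11 brings subjects with ALT or AST above 3 x ULN back within 72 hours of the result for confirmatory testing.
- **Phase of the transition.** SAP 9.4 summarises laboratory data separately by phase. SAP 3.3 says: "Between the study phases, Cohort 2 has a 2-week, blinded, step transition for placebo subjects to ganaxolone". The transition tables in SAP 9.1 and Protocol 9.1 place the same days in Phase 2.

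**The concern.** A mid-point window labels a record correctly only if treatment is the same on both sides of the visit. Here treatment changes at the visit itself, so the later half of the window belongs to a different treatment or dose. For summary tables, the last-record rule then prefers the later sample.

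Visit 5 is the last placebo-controlled laboratory assessment. If a placebo subject has a further sample in the days after Visit 5, the plan as written can report a value taken on ganaxolone as that subject's end-of-double-blind placebo value, or let it set the shift category. In Cohort 1, a value taken on 1800 mg/d can appear in the Visit 4 row, which is meant to describe 1200 mg/d.

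**Working it through.** **Inputs.** Visit weeks come from Protocol 9.5.5 (for example "Visit 3 (Up-Titration; Cohort 1: Week 1; Cohort 2: Week 2"). Dosing days come from Protocol Tables 1 and 2.

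**Reproducing the plan's day labels.** Study day = 7 x week + 1 gives the table labels exactly:
- Cohort 1: Visit 3 (week 1) day 8; Visit 4 (week 5) day 36; Visit 5 (week 9) day 64; Visit 6 (week 10) day 71.
- Cohort 2: Visit 3 (week 2) day 15; Visit 4 (week 8) day 57; Visit 5 (week 14) day 99; Visit 6 (week 16) day 113.

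**Windows.** Lower bound = (previous visit day + visit day)/2. Upper bound = (visit day + next visit day)/2.

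| Window | Lower | Upper | First dose after the change | Days in window from that dose |
|---|---|---|---|---|
| Cohort 2 Visit 5 | (57+99)/2 = 78 | (99+113)/2 = 106 | day 99, placebo to ganaxolone | 99-106 = 8 |
| Cohort 1 Visit 5 | (36+64)/2 = 50 | (64+71)/2 = 67.5 | day 64, placebo to ganaxolone | 64-67 = 4 |
| Cohort 1 Visit 4 | (8+36)/2 = 22 | (36+64)/2 = 50 | day 36, 1200 to 1800 mg/d | 36-50 = 15 |

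These counts include the visit day, when the scheduled sample may precede the first new dose. Without it they are 7, 3 and 14.

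**Sensitivity.**
- With day = 7 x week, the overlaps are 7, 3 and 14 days.
- Protocol 9.5.5 allows Visit 5 to vary by 3 days. If it is 3 days early and the switch follows it, with windows at nominal days, the overlaps become 96-106 = 11 days (Cohort 2) and 61-67 = 7 days (Cohort 1). If it is 3 days late, they become 102-106 = 5 and day 67 only = 1.

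The crossing exists under every convention tried.

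**Which records can fall there.** Appendix 1 schedules no laboratory draw between Visits 5 and 6, or between Cohort 1 Visits 4 and 5. Only an unscheduled, repeat or early-termination sample can do so. Take a liver-enzyme recheck prompted by the Visit 5 sample. If the result takes 0 to 4 days (assumed; the documents give no turnaround), the recheck falls by day 99 + 4 + 3 = 106 in Cohort 2, inside the window. In Cohort 1 the room is smaller: result time plus recheck time must not exceed 3 days (64 + 3 = 67).

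**What the rules do with such a record.** In summary tables it is the last record and replaces the scheduled value. In shift tables it matters only if it is worse than the scheduled value and crosses a reference limit.

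**Effect of the correction.** With the windows cut at the change, no day after the switch remains in the placebo Visit 5 windows, and no day at 1800 mg/d remains in the Cohort 1 Visit 4 window.

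**The case against.** The strongest reply is that the phase split already deals with this. SAP 9.4 reports laboratory data by phase, and no passage puts the transition inside the double-blind phase. Between the phases is not double-blind, and the SAP 9.1 tables and Protocol 9.1 say Phase 2. On that reading a transition record never reaches a double-blind table.

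This stands in part. It works only if records are split at the first transition dose before windows are applied, and the SAP gives no such date rule. Until it does, the window says Visit 5 and the phase label says open-label or neither, so two programmers could place the record differently. The phase split also cannot help at Cohort 1 Visit 4, which lies wholly inside the double-blind phase.

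Other parts of the reply stand in full:
- **Frequency.** A reader might infer that many placebo values would be replaced. The documents give no rate of repeat testing. Protocol 7 reports LFT rises above 3 x ULN in under 1% of ganaxolone-treated subjects and gives no placebo figure. Taking 1% as an assumed placebo ceiling, that trigger alone would involve fewer than 2 of 178 subjects (0.01 x 178 = 1.78). Other repeats are optional.
- **Direction.** A reader might infer a bias towards no difference. That is not shown: a confirmatory repeat can be higher or lower, and an analyte already high at Visit 5 cannot move to a worse category on retest. Only another analyte in the panel, or a normal value retested, could change category.
- **Cohort 1 dose comparison.** A reader might infer that the dose-level safety comparison is compromised. The adverse-event split uses onset weeks, and laboratory data are not summarised by dose level. Only the by-visit laboratory results in the ganaxolone arm are touched.

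**Conclusion.** The point holds as a defect in a stated rule with limited reach. The windows cross a treatment change by 8 days (Cohort 2 Visit 5), 4 days (Cohort 1 Visit 5) and 15 days (Cohort 1 Visit 4), counting the visit day. The laboratory selection rules can then report a post-change value under a pre-change label.

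The scope is by-visit laboratory summaries and laboratory shift tables. Seizure endpoints use diary counts over whole periods and adverse events are assigned by onset, so neither depends on these windows.

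The conclusion rests on reading SAP 6.4 literally and on at least some unscheduled or early-termination samples falling in those days. How many there would be, and which way they would move a comparison, cannot be derived from the documents; the number is probably small. The point ranks between minor and advisable. It is worth correcting because the correction is nearly free and the end-of-double-blind laboratory table should contain only values taken on the randomised treatment.

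**What to change.** Analysis wording only; no dose, visit or clinical rule changes.

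1. In SAP 6.4, state that no window crosses a treatment change. End the Visit 5 window before the first transition dose and the Cohort 1 Visit 4 window before the first 1800 mg/d dose. Assign later records to the next visit.
2. Keep the scheduled Visit 4 or Visit 5 sample with its own visit when it carries the same date as the first new dose but was taken before it.
3. In SAP 3.3, assign the transition to the open-label phase for all by-phase safety tables, in line with Protocol 9.1 and the SAP 9.1 table headings.
4. In SAP 9.4, apply the last-record and worst-value rules only within the truncated windows.

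The cost is a few sentences and one date comparison in the analysis-dataset code, using dose dates from the study drug log that SAP 9.1 already uses for exposure. No new data are needed. The change is best made before the double-blind database lock.
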